4 STUDY DESIGN

4.1 OVERALL DESIGN

We hypothesized that cognitive training *EndeavorRx* may augment cognitive control and reduce depressive symptoms. In this study, youth with subclinical depressive symptoms (ages 9 to 17) will be recruited to complete the CCT intervention for 4-weeks. Before and after the intervention, all participants will complete semi-structured clinical assessment of depressive symptoms and a computerized evaluation of cognitive control capacity (e.g., Millisecond Inquisit Web Cognitive Battery; Zelazo, Anderson, Richler, Wallner-Allen, and Beaumont, 2013)

Recruitment will leverage a well-characterized sample from a recently completed study (“Parent study”; HUM00118950) of clinically significant anxiety, a known risk factor for emergence of later depressive symptoms in the subclinical-to-clinical range. In the Parent study, 148 youths (7-17 years) with impairing anxiety were recruited and randomized 2:1 to receive 12-week CBT or a non-active control therapy, “relaxation and mentorship therapy” (RMT); behavioral, neurobiological (fMRI), and clinical measures were collected before and after treatment. Additional participants may need to be recruited beyond the “Parent study” sample (for reasons such as: slow recruitment from “Parent study” or not enough participants from “Parent study” meeting enrollment criteria).

Up to thirty subjects from the Parent study will be recruited to complete the *EndeavorRx* intervention. The intervention will be played at home for ~25 min/day), 5x per week, for 4 weeks. Designed as an exciting, youth-friendly computer game, *EndeavorRx* engages and trains cognitive control across component processes of attention, response inhibition, shifting and working memory. Of note, *EndeavorRx* game difficulty is titrated to individual performance, and thus age; the increasing difficulty helps to reduce participant boredom and progressively train cognitive control. Adherence to prescribed training will be monitored using an Akili-provided dashboard, available to the research study team, that interfaces real-time as participants access *EndeavorRx* via their iPads. If there is no game play for ≥48 hours, a parent will be contacted in order to ensure compliance with the intervention.

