If the Parent study does not yield sufficient participation, then we will recruit through the community using the social media campaign strategies that have proven effective in our past work, including UMHealthResearch. The proposed study will add up to three additional timepoints of assessment (pre-intervention, post-intervention, and (if applicable) 3-months post-intervention. All study activities will be completely remotely via an encrypted HIPAA-compliant video conferencing platform (e.g., Zoom), phone

call, and/or Qualtrics links. Depressive symptoms, anxiety symptoms, general psychopathology, and cognitive control behavior as indexed by a *Millisecond Inquisit Web* Cognitive Battery will be assessed pre-intervention. After the intervention, the same symptoms and cognitive control behavioral will be assessed. These variables will optionally be assessed again 3-months post intervention.

Data analyses will compare pre- and post-CCT data. Additionally, multilevel models will assess change in depressive symptoms and cognitive control over time and comparing between those who received CBT as compared to those who received RMT in the Parent study. These data will include *Millisecond* measures of behavioral capacity for cognitive control and detailed assessment of depressive and anxiety symptoms using both clinician-interview and self-report. Pre- to post-CCT change in depressive symptom severity (clinician-measured) will serve as the primary outcome variable.

At protocol version 2.1 (02 April 2024), Assessment #3 (3-month follow-up) was removed to increase feasibility so that resources could focused on increased recruitment.

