4.4 END-OF-STUDY DEFINITION

A participant is considered to have completed the study if he or she has completed the baseline assessment, at least 4 weeks of CCT intervention, *Millisecond* battery, post-intervention assessment, and

the final assessment. If a participant completes all these activities but not the final, optional (3-month post-intervention) assessment, then they will, at PI discretion, still be considered to have completed the study. In other words, if a participant does not participate in Assessment #3, they will still be considered to have completed the study. At protocol version 2.1 (02 April 2024), Assessment #3 (3-month follow-up) was removed altogether.

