7.2 PARTICIPANT DISCONTINUATION/WITHDRAWAL FROM THE STUDY

Participants are free to withdraw from participation in the study at any time upon request. An investigator may discontinue a participant from the study for the following reasons:

- Significant study intervention non-compliance, such as not engaging in the video game intervention at all (compliance will be monitored in real-time using Akili software).
- Lost-to-follow up; unable to contact subject (see **Section 7.3, Lost to Follow-Up**)
- Any event or medical condition or situation occurs such that continued collection of follow-up study data would not be in the best interest of the participant or might require an additional treatment that would confound the interpretation of the study
- The participant meets an exclusion criterion (either newly developed or not previously recognized) that precludes further study participation
- The study is suspended or canceled

The reason for participant discontinuation or withdrawal from the study will be recorded. Subjects who sign the informed consent form but do not receive the study intervention, may be replaced. Subjects who sign the informed consent form and receive the study intervention, and subsequently withdraw, or are discontinued from the study, will be replaced.

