9.2 SAMPLE SIZE DETERMINATION

Sample size was determined based on results from a power analysis and feasibility of participant recruitment. A sample size of 32 participants would yield 80% power for the planned analyses in the current study, but 30 participants is a more achievable initial target for recruitment. Though there is minimal data

to generate hypothesized effect sizes, the proposed study will allow for generations of effect sizes to be used in future, larger studies.

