9.4.6 PLANNED INTERIM ANALYSES

At Time 2, after the completion of the CCT intervention, CDI scores will be evaluated across all participants. If scores are significantly worse at Time 2 than at Time 1 (a significantly higher average CDI score across participants), then the study may be halted. Similarly, if greater than one third of the participants (~7 subjects) withdraw from the study due to symptoms, then the study may be halted. If there is no change, or an improvement in CDI scores (lower CDI scores), then the study will continue as planned. This interim analysis will be conducted with the intention of maintaining safety of participants, rather than for assessing the efficacy of the intervention.

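### Section 9.4.6 equates more than one third of participants with about 7, but at the planned 30 it means at least 11 (minor; wrong as written)

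*Combined protocol and SAP*

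**What the plan says.** Section 9.4.6 gives two grounds on which the study may be stopped for safety.

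- **Withdrawals:** "if greater than one third of the participants (~7 subjects) withdraw from the study due to symptoms, then the study may be halted".
- **Group CDI comparison:** "At Time 2, after the completion of the CCT intervention, CDI scores will be evaluated across all participants". A significantly higher mean than at Time 1 may lead to a halt. If CDI scores are unchanged or lower, the study goes on. The section states that the purpose is safety, not efficacy.

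The sample size comes from 9.2: "A sample size of 32 participants would yield 80% power", "but 30 participants is a more achievable initial target for recruitment". Section 4.1 adds "Up to thirty subjects from the Parent study will be recruited to complete" the intervention. That is a ceiling on recruits from the Parent study, since the same section allows others to be added, so the target of 30 rests on 9.2.

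Two other provisions bear on the rule. Under 7.2, participants who received the intervention and "subsequently withdraw, or are discontinued from the study, will be replaced". On the visit schedule, 4.4 records: "At protocol version 2.1 (02 April 2024), Assessment #3 (3-month follow-up) was removed altogether". Assessment 2 is therefore now the last assessment.

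**The concern.** A halting rule should give one answer for any set of data. This one states a fraction and a count as though they were the same, and at the planned size they differ by four participants. Someone applying the count would bring the study up for a possible halt at 7 symptom withdrawals. Someone applying the fraction would wait for 11. Of the two grounds in 9.4.6, this is the only one expressed as a number of participants, and the participants are minors with depressive symptoms, so the threshold should be unambiguous before it is needed.

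The group CDI look raises a lesser question. It is placed at Time 2 across all participants, but nothing says how many must have completed Assessment 2, or by what date, before it is done.

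**Working it through.** **Inputs.** Fraction: more than 1/3 (9.4.6). Stated count: about 7 (9.4.6). Planned N: 30 as target, 32 for 80% power (both 9.2). Symptom-withdrawal rate: not given, so assumed below.

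**Step 1. Try to reproduce the count of 7.** The smallest whole number strictly above N/3 is floor(N/3) + 1.

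- N = 30: 30/3 = 10, so at least 11 (11/30 = 36.7%).
- N = 32: 32/3 = 10.67, so at least 11 (11/32 = 34.4%).
- Reading the rule loosely as one third or more, N = 30 gives 10 and N = 32 gives 11.

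None of these is close to 7. As percentages, 7/30 = 23.3% and 7/32 = 21.9%.

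**Step 2. Find the N that 7 would fit.**

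- Seven is the smallest count above one third for N = 18, 19 and 20 (18/3 = 6, 19/3 = 6.33, 20/3 = 6.67).
- N/3 rounds to 7 for N = 20, 21 and 22 (6.67, 7, 7.33).

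So the count fits a sample of about 18 to 22. No section states such a size, whether as enrolled, evaluable or interim.

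**Step 3. How often would the two readings disagree?** They disagree when 7 to 10 of 30 withdraw for symptoms. Take a fixed 30 treated, each withdrawing independently with probability p, so that X is binomial(30, p) and P(7 ≤ X ≤ 10) = P(X ≥ 7) − P(X ≥ 11).

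| Assumed p | P(X ≥ 7) | P(X ≥ 11) | P(7 to 10) |
|---|---|---|---|
| 10% | 0.0258 | 0.0001 | 0.0257 (2.6%) |
| 20% | 0.3930 | 0.0256 | 0.3674 (37%) |
| 30% | 0.8405 | 0.2696 | 0.5709 (57%) |

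**Step 4. Effect of replacement.** Section 7.2 replaces treated participants who withdraw. If w withdraw for symptoms and recruitment continues until 30 are retained, 30 + w have been treated. If all of them count, more than one third means w > (30 + w)/3, that is 2w > 30, so w is at least 16 (16/46 = 34.8%; 15/45 is exactly one third). If the denominator stays at 30, the threshold stays at 11. The protocol does not say which applies, so the fraction alone does not fix a count either.

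**Step 5. Timing of the CDI look.** Section 9.4.6 gives a visit (Time 2) and a population (all participants), but no calendar point and no number of completers. Taken literally, the look would wait until every participant had finished both the training and what is now the last assessment.

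**The case against.** On the withdrawal count, the best defence is that the figure is marked as approximate and sits in brackets, so the fraction should govern. The approximation sign does not cover a gap of four participants in a threshold of 11, and the text does not say which expression governs. Another defence is that a sample near 20 was meant. That is possible, but no section says so.

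On consequence, the defence is stronger and stands. Both grounds are discretionary. Section 7.1 discontinues an individual whose CDI rises by more than 25%, who endorses the suicidality item or who is hospitalised for psychiatric symptoms. Section 10.1.2 allows suspension for unacceptable risk, 10.1.6 sets biweekly team review, and 10.1.7 adds a check after each participant's assessment and at least weekly review of flagged responses. The written count of 7 is also the more cautious of the two readings.

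On the CDI look, a reader might infer that removing Assessment 3 has pushed the comparison to the end of the study, leaving nothing to halt. The documents do not establish that. The section calls itself an interim analysis and provides for the study to continue afterwards. Time 2 can be read as each participant's own visit under staggered entry. Section 9.2 calls 30 an initial target, so a look after the first 30 could still stop further enrolment. Even under the literal reading, training would already have been over for everyone before version 2.1, with only an optional follow-up visit remaining. What stands is narrower: the timing is not specified, and one permissible reading makes the look too late to be useful.

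**Conclusion.** The withdrawal trigger is wrong as written. At 30 or 32 participants, more than one third is at least 11, not about 7. This part is plain arithmetic on the protocol's own figures. How often the discrepancy would matter depends on a withdrawal rate that the protocol does not give: the 2.6%, 37% and 57% are illustrations at assumed rates of 10%, 20% and 30%, with a fixed 30 treated and independent withdrawals. No probabilities are given for the replacement case, because they would depend on a denominator that the protocol leaves open.

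The CDI look is a secondary point about missing detail, not an error. It is for safety only, so no efficacy error rate is at stake. A reader might also infer that participants are left unprotected; the individual rules and team review show otherwise. Overall this is a minor correction, but worth making because a stated decision threshold cannot be applied consistently.

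**What to change.** In 9.4.6, replace the fraction and bracketed count with one threshold and its denominator. Either of these would do:

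- at least 11 of 30 participants who started the training; or
- at least 7 of 30 (about 23%), if the team prefers the more protective trigger.

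The choice is the study team's. Seven prompts review earlier; 11 of a fixed 30 would be reached only 27% of the time at an assumed true rate of 30%. State whether participants replaced under 7.2 stay in the denominator. It would also help to say whether a discontinuation under 7.1 for a CDI rise above 25% counts as a withdrawal due to symptoms.

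For the group CDI comparison, name the number of completed Assessment 2 visits at which it will be done, chosen so that enrolment is still open. If no such look is wanted, delete that ground and rely on 7.1 and 10.1.7.

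The cost is a few sentences in a protocol amendment and, if the CDI look is kept, one short summary of data already being collected. No extra visits or participants are needed.

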9.4.7 SUB-GROUP ANALYSES

The sample included in this pilot study will not be large enough to conduct subgroup analyses based on sex or race/ethnicity. However, if applicable, in the secondary endpoint models, age and sex may be included as covariates. The current analyses will assess the efficacy of the study intervention in youth only (ages 9-17).

9.4.8 TABULATION OF INDIVIDUAL PARTICIPANT DATA

All clinical and behavioral measures will be listed by timepoint when applicable.

9.4.9 EXPLORATORY ANALYSES

Linear regression models will be built to test whether change in cognitive control indices (behavioral performance on *Millisecond* battery) will associate with change on clinical outcomes (CDI or CDRS-R scores). The standardized parameter estimates in each model will be examined.

10 SUPPORTING DOCUMENTATION AND OPERATIONAL CONSIDERATIONS

10.1 REGULATORY, ETHICAL, AND STUDY OVERSIGHT CONSIDERATIONS

10.1.1 INFORMED CONSENT PROCESS

10.1.1.1 CONSENT/ASSENT AND OTHER INFORMATIONAL DOCUMENTS PROVIDED TO PARTICIPANTS

Consent forms describing in detail the study intervention, study procedures, and risks will be given to the participant and electronic documentation of informed consent will be completed prior to starting the study intervention. The following consent materials are submitted to IRBMED with this protocol: Assent Form and a Parent-only Consent Form to accompany the child Assent Form.

10.1.1.2 CONSENT PROCEDURES AND DOCUMENTATION

The protocol will begin by having the subject (or their parent[s]/guardian[s] for adolescent subjects) provide assent and informed consent. Informed consent will be obtained at the beginning of a remote visit. This remote visit will include a review of an oral assent script, assent from the minor subject, and signed electronic consent from their parent/guardian. Electronic informed consent signatures will be collected using SignNow. All procedures will adhere to the IRBMED Guidance for use of SignNow for Electronic Informed Consent Procedures. Informed consent is a process that is initiated prior to the individual's agreeing to participate in the study and continues throughout the individual's study participation. Extensive discussion of risks and possible benefits of this intervention will be provided to the subject/parents. Consent forms (written in non-technical language, understandable by the youngest subject to be enrolled in the study) describing in detail the study interventions/products, study procedures, and risks will be given to the subject/parent. Participants may also be presented with a visual timeline of the tasks that may be involved in participating in this study, during the consenting process or at another time during the study, to aid their understanding of the process. Upon reviewing the document, one of the investigators (or their designee) will explain the research study to the subject/parent and answer any questions that may arise.

All youth subjects will be given an assent form and/or will be read an assent script by study staff. The parent will sign the parental informed consent document prior to any procedures being done specifically for the study, besides the prescreen questions on UMHealthResearch and/or initial phone screen, which is conducted with the parent. Youth subjects will be asked to sign in the assent box on the assent form written in language that is developmentally appropriate for their understanding of study participation, along with parent signature on the parental consent form. Children under age 10 (age 9) will be read an assent script by study staff and will not have to sign the document, but to verbally give assent and study staff will indicate their assent and sign the document. If the child wishes to sign, they may do so. For all subjects, parents will sign a separate parent consent form. All subjects or their parents may withdraw consent at any time throughout the course of the trial. A copy of the parental informed consent and child assent documents will be given to the subjects for their records.

The subjects may withdraw consent at any time throughout the course of the trial. The rights and welfare of the subjects will be protected by emphasizing that the quality of their medical care will not be adversely affected if they decline to participate in this study. NOTE: older teens may become legal adults (i.e., reach the age of 18 years) during the course of the study. If the teen is still actively involved in the study (i.e., data collection ongoing), then a new consent form, signed by the teen, will be obtained. However, if the teen reaches 18 years of age *after* their data collection has been completed, we will *not* re-contact to re-consent. This approach is intended to avoid burdening study participants and their parents.

10.1.2 STUDY DISCONTINUATION AND CLOSURE

This study may be temporarily suspended or prematurely terminated if there is sufficient reasonable cause. Reasons for discontinuation will be document, and all outcome assessments will proceed as scheduled, if possible. If the study is prematurely terminated or suspended, the Principal Investigator (PI) will promptly

inform study participants, the Institutional Review Board (IRB), and sponsor/funding agency and will provide the reason(s) for the termination or suspension. Study participants will be contacted, as applicable, and be informed of changes to study visit schedule.

Circumstances that may warrant termination or suspension of CCT include, but are not limited to:

- Hospitalization required for any psychiatric symptoms
- Suicide behaviors during the study period (assessed by CDI and CDSRS post-intervention)
- Determination of unexpected, significant, or unacceptable risk to participants
- Data that are not sufficiently complete and/or evaluable

The study may resume once concerns about safety, protocol compliance, and data quality are addressed, and satisfy the funding agency and IRB.

10.1.3 CONFIDENTIALITY AND PRIVACY

Participant confidentiality and privacy is strictly held in trust by investigator, research staff, and the sponsor(s) and funding agency. This confidentiality is extended to the data being collected as part of this study. Data that could be used to identify a specific study participant will be held in strict confidence within the research team. No personally-identifiable information from the study will be released to any unauthorized third party without prior written approval of the sponsor/funding agency.

All research activities will be conducted virtually, but in as private a setting as possible, so that participants feel comfortable to share details about their symptoms to the assessing clinician.

Other authorized representatives of the sponsor or funding agency, representatives of the Institutional Review Board (IRB), or regulatory agencies may inspect all documents and records required to be maintained by the investigator, including but not limited to, medical records (office, clinic, or hospital) and pharmacy records for the participants in this study. The research team will permit access to such records.

The study participant's contact information will be securely stored for internal use during the study. At the end of the study, all records will continue to be kept in a secure location for as long a period as dictated by the reviewing IRB, Institutional policies, or sponsor/funding agency requirements.

All paper and computer research records will be identified by subject ID number rather than name or other personally identifying information. Paper records are stored in a double-locked environment to which only authorized study team members have access. The link between subject ID and subject name will be kept within a secure study folder (only primary research team members have access; requires Level-2 Login) that can only be accessed on computers that are password protected. Consent documents and any other forms with identifying information will be maintained separately from research data files (identified by subject ID only).

The assessments in this protocol will ask participants about sensitive topics, such as mental illness and substance use. We will inform the consenting parents of minor participants at the beginning of the process that we will respect the confidentiality of all participants. It is important for us to let participants know that they can be honest about sensitive topics without fear of reprisal from their parents. However, all participants will also be informed about limits to confidentiality. If we learn that a subject has potential to harm him or herself, or another individual, we will break confidentiality and take steps to prevent harm. Similarly, any evidence of potential child abuse will be reported to Child Protective Services. If we become

aware of imminent risk of harm to a parent, steps will be taken to ensure safety (e.g. referral to psychiatric emergency services or contacting appropriate authorities).

